		5.9.1 Receipt of Drug Supplies	
		5.9.3 Dispensing of Study Drug	
		1.9.3 Dispensing of Study Drug	
,		STUDY PROCEDURES.	
6			_
	6.1	VISIT 1	
	6.2 6.3	VISIT 2	
7			
7		STATISTICAL PLAN	
	7.1	SAMPLE SIZE DETERMINATION	
	7.2 7.3	STATISTICAL METHODS	
_			
8	S	SAFETY AND ADVERSE EVENTS	
	8.1	DEFINITIONS	
	8.2	RECORDING OF ADVERSE EVENTS	26

Venofer® use in POTS Version5 Revised 06/02/16 8.5 Stopping Rules 27 8.6 Medical Monitoring 27 8.6.1 DATA HANDLING AND RECORD KEEPING.......28 9.1 9.3 STUDY MONITORING, AUDITING, AND INSPECTING29 STUDY MONITORING PLAN 29 10.2 ETHICAL CONSIDERATIONS.......30 12 12.1 FUNDING SOURCE 30 12.2 12.3 SUBJECT STIPENDS OF PAYMENTS 30 13

REFERENCES31

14

List of Abbreviations

LIST OF ABBREVIATIONS

AE Adverse Event/Adverse Experience

CFR Code of Federal Regulations

CRF Case Report Form

DSMB Data and Safety Monitoring Board FDA Food and Drug Administration

GCP Good Clinical Practice

HIPAA Health Insurance Portability and Accountability Act

IB Investigator's Brochure

IND Investigational New Drug Application

IRB Institutional Review Board PHI Protected Health Information

PI Principal Investigator

SAE Serious Adverse Event/Serious Adverse Experience

SOP Standard Operating Procedure

Study Summary

Title	A Randomized, Controlled, Double-Blind, Placebo-Controlled Study Evaluating the Efficacy of Intravenous Iron Sucrose in Adolescents with Non-anemic Iron Deficiency and Postural Orthostatic Tachycardia Syndrome (POTS)			
Running Title	Iron Sucrose in Adolescents with Iron Deficiency and POTS			
Protocol Number	12-009963			
Phase	Phase II			
Methodology	Randomized, controlled, double-blind, placebo-controlled			
Overall Study Duration	Expected duration of 2 years			
Subject Participation Duration	Six months			
Single or Multi-Site	Single center			
Objectives	 To assess whether a single infusion of iron sucrose will improve orthostatic symptoms as measured by a validated survey instrument in adolescent subjects with POTS and non-anemic iron deficiency To assess whether a single infusion of iron sucrose will improve cardiovascular indices, specifically a reduction in the intraval of measured heart rate change, during a ten minute head up tilt, in adolescent subjects with POTS and non-anemic iron deficiency To determine if abnormalities in standing and supine catecholamine levels will improve following intravenous iron sucrose infusion in adolescent subjects with POTS and non-anemic iron deficiency 			
Number of Subjects	30			
Diagnosis and Main Inclusion Criteria	Adolescent subjects 12-21 years of age who have a diagnosis of Postural Orthostatic Tachycardia Syndrome and non-anemic iron deficiency as defined by a serum ferritin level of less than or equal to 20 ug/L			
Study Product, Dose, Route, Regimen	5 mg/kg of intravenous iron sucrose supplied as Venofer ® (maximum dose of 200 mg). Iron sucrose will be diluted to 1 mg of elemental iron in 1 mL of NaCl 0.9% (maximum volume of 210 mL).			
Duration of Administration	Single dose administration			
Reference therapy	Normal saline (NaCl 0.9%) 5 mL/kg (maximum volume 210 mL)			

Version5

	Data will be visually inspected for normality. Group comparisons will
	include Fisher's exact test for categorical variables and Wilcoxon rank
Statistical	sums for continuous variables. Confidence intervals will be calculated
Methodology	at 95%. All P-values will be 2-sided with values less than 0.05
	considered significant. All analyses will be performed on an "intention
	to treat" basis.

1 Introduction

This document is a clinical research protocol for a human research study. This study will be carried out in accordance with the applicable United States government regulations and Mayo Clinic research policies and procedures.

1.1 Background

Postural orthostatic tachycardia syndrome (POTS) is characterized by an exaggerated heart rate response to the standing position in a patient with symptoms of orthostatic intolerance [1]. It is likely a heterogeneous disorder representing a common manifestation of a number of possible underlying derangements such as impaired sympathetically mediated vasoconstriction, excessive sympathetic drive, volume dysregulation and deconditioning [2]. POTS was first described in the literature by Low and Schondorf in 1993 and was recognized in adolescent by Stewart et al. in 1999 [3, 4] While the actual prevalence of POTS is unknown, it has been estimated to affect at least 500,000 individuals in the United States [5]. It predominately affects young individuals, and particularly women [6].

The prevalence of iron deficiency in adolescents with POTS has been reported to be greater than that expected in the general adolescent population [7, 8]. Iron is an essential element in both cellular and enzymatic function. Iron deficiency is one of the most common nutritional deficiencies noted worldwide [9]. Iron deficiency has been estimated to affect nearly 7.8 million adolescent girls and women of childbearing age in the United States [8]. Iron deficiency has been linked to numerous clinical findings in children and adolescents including decreased motor activity, social inattention, delayed cognitive development, neurally mediated syncope, restless legs syndrome and chronic fatigue [7, 9, 10]. Iron supplementation in non-anemic, iron-deficient adolescent girls has demonstrated improvements in cognitive functioning [11]. A double-blinded, placebo-controlled trial demonstrated a reduction of chronic fatigue symptoms following intravenous iron administration in iron deficient, non-anemic patients [12]. A similar study showed a reduction in symptoms of restless leg syndrome following iron infusion for iron-deficient patients [13].

Interestingly, elevations in urine and blood catecholamine levels have been described in non-anemic iron deficient animal models [14]. Similar urine catecholamine elevations were found in children with iron deficient anemia [15]. An adult study demonstrated elevated serum catecholamines levels in iron deficient patients with anemia, and found that anemia from other causes had no significant increase in plasma catecholamine levels [16]. While the pathophysiology of catecholamine synthesis, function and degradation is still not fully understood, it is possible that iron may be an integral component, given its ubiquitous role in enzyme function. Catecholamine derangements have been found in patients diagnosed with POTS, thus there may be a correlation between iron deficiency and POTS.

Adolescence is a complex time of physical, emotional, social, cognitive and moral development [17]. These changes are paralleled by transitions from parental to self-management for health care related issues. Although adolescents are increasingly responsible for their health care

decisions, there is an extensive literature highlighting poor medication adherence in this population [18]. Oral iron supplements, in particular, are commonly discontinued due to patient complaints of gastric irritation and lack of palatability [19]. In part given these limitations, intravenous iron supplementation has been used clinically for correction of iron deficiency in select adolescent patients who are otherwise healthy.

The use of intravenous iron sucrose has been shown to be a safe and effective therapy for correcting iron deficiency in children and adolescents [20, 21]. Iron sucrose administered at a dose of 7 mg Fe/kg, up to a maximum dose of 300 mg of iron sucrose, has been shown to be well-tolerated in children and adolescents [20]. Adult data have found similar safety and limited side effects with single intravenous doses less that 300 mg of iron sucrose [22].

Anecdotal experience at our clinic has demonstrated an immediate reduction in self-reported orthostatic symptoms in several patients diagnosed with POTS following the administration of intravenous iron sucrose for iron deficiency.

1.2 Investigational Agent

The following text in this section 1.2 is taken directly from the Drug Summary available on MD Consult. This information was last updated September 28, 2012[23]:

Description: Iron sucrose is an intravenous iron formulation approved for the treatment of iron deficiency anemia in patients with chronic kidney disease. Iron sucrose is one of the oldest parenteral iron preparations available; it has been used clinically for more than 50 years. Parenteral iron is preferred over oral iron therapy when rapid repletion of iron-depleted patients is desired. Intravenous iron has been used to treat the anemia associated with dialysis and may reduce the need for erythropoietin dosage by about 40%[24]. Iron sucrose contains ferric hydroxide complexed with sucrose; this complex has a molecular weight of 34,000—60,000 daltons. This compound is free of ferrous ion and dextran polysaccharides. In contrast, iron dextran consists of a complex of ferric oxyhydroxide with dextrans. Parenteral iron sucrose (Venofer®) and iron gluconate (Ferrlecit®, see separate monograph) appear less likely to cause hypersensitivity reactions than iron dextran[25], and have been used in patients with a hypersensitivity to iron dextran[26-28]. However, hypersensitivity may occur with iron sucrose also; serious and fatal anaphylactic reactions have been reported. Intravenous iron sucrose rapidly increases serum iron concentrations, which can be reliably measured 48 hours after administration. Iron sucrose complex (Venofer) was originally approved by the FDA for administration by slow IV injection or IV infusion in November 2000 in adult patients with iron deficiency anemia and chronic kidney disease requiring hemodialysis who are receiving supplemental erythropoietin therapy. In June 2005, the FDA approved iron sucrose for the treatment of iron deficiency anemia in non-dialysis dependent adult patients with chronic kidney disease, and in October 2005, the FDA approved iron sucrose for the treatment of iron deficiency anemia in adult patients with chronic kidney disease on peritoneal dialysis who are receiving supplemental erythropoietin therapy. In September 2012, iron sucrose was approved for iron maintenance treatment in pediatric patients >= 2 years with iron deficiency anemia and chronic

Venofer® use in POTS

Version5

Revised 06/02/16

kidney disease who require hemodialysis, peritoneal dialysis, or are non-dialysis dependent and are receiving supplemental erythropoietin therapy[28].

Mechanism of Action: Normal erythropoiesis depends on the concentration of iron and erythropoietin available in the plasma, both being decreased in renal failure. Exogenous administration of erythropoietin increases red blood cell production and iron utilization, contributing to iron deficiency in hemodialysis patients. Intravenous iron has been used to treat the anemia associated with hemodialysis and may reduce the need for erythropoietin dosage by about 40%. Following IV administration of iron sucrose, the complex of polynuclear iron (III)-hydroxide in sucrose is dissociated into iron and sucrose by the reticuloendothelial system. In addition, a competitive exchange of iron takes place from the iron sucrose complex to the iron-binding protein transferrin. A therapeutic response to treatment with iron therapy is dependent upon the patient's iron stores and the ability to use the iron. Use of iron is influenced by the cause of the deficiency as well as other illnesses that can affect normal erythropoiesis. Protein-energy malnutrition can prevent the incorporation of iron into the erythrocyte regardless of the quantity of iron stored. Only when lean body mass expands will iron be used. Iron therapy alone does not increase red blood cell production. Administration of iron only improves anemia which is associated with iron deficiency.

Iron-containing proteins and enzymes are important in oxidation-reduction reactions, especially those of the mitochondria. Iron is a component of myoglobin and several heme-enzymes, including the cytochromes, catalase, and peroxidase. Iron is an essential component of the metalloflavoprotein enzymes and the mitochondrial enzyme alpha-glycerophosphate oxidase. Iron-containing proteins and enzymes are important in oxidation-reduction reactions, especially those of the mitochondria. Furthermore, iron is a cofactor for enzymes such as aconitase and tryptophan pyrrolase. Iron deficiency not only causes anemia and decreased oxygen delivery, it also reduces the metabolism of muscle and decreases mitochondrial activity. Iron deficiency can also lead to defects in learning or thermoregulation. Thus iron is important to several metabolic functions which are independent of its importance to erythropoiesis.

Pharmacokinetics: Iron sucrose is administered intravenously. In healthy adults receiving IV doses of iron sucrose, its iron component appears to distribute mainly in blood and to some extent in extravascular fluid. A significant amount of the administered iron distributes in the liver, spleen and bone marrow. The bone marrow is considered an iron trapping compartment and not a reversible volume of distribution. Following IV administration, iron sucrose is dissociated into iron and sucrose by the reticuloendothelial system. The sucrose component is eliminated primarily by urinary excretion (75.4% in 24 h). Approximately 5% of the iron is excreted in the urine over 24 hours. In healthy adults treated with IV iron sucrose, the iron component exhibits linear kinetics with an elimination half-life of about 6 hours and a systemic clearance of 1.2 L/h.

Iron therapy dosage is individualized according to patient goals for serum iron levels, iron storage parameters (e.g., ferritin, transferrin saturation) and serum hemoglobin concentrations. Iron toxicity may occur with excessive or unnecessary iron therapy. Systemic iron is stored in compounds called ferritin and hemosiderin, which are used for future use in the production of hemoglobin. The absorption of iron depends upon the route of entry. The tissue that first clears parenterally administered iron from the bloodstream determines the bioavailability. If the

reticuloendothelial system clears iron, only small amounts will be available over time to the bone marrow. Transferrin accepts iron from the intestinal tract or from sites of storage or hemoglobin destruction. Iron is then transported in plasma bound to transferrin and distributed to the bone marrow for hemoglobin synthesis, to the reticuloendothelial system for storage, to all cells for enzymes containing iron and to placental cells if needed to meet fetal needs. Transferrin eventually becomes available for reuse. There is no destructive metabolism of iron because it takes place in a closed system. In normal adults, ninety percent of metabolized iron is conserved and reutilized repeatedly. Very little iron is eliminated. In normal, healthy adults, some daily loss

of iron occurs through normal skin, hair, and nail loss, and GI losses. Menstruating women have

•Special Populations

an increased loss as do other persons with loss of blood.

Pediatrics

Following a single-dose of iron sucrose 7 mg/kg (max = 200 mg) in patients 12-16 years (n = 11) with non-dialysis dependent chronic kidney disease, mean AUC was 31305 mcg x h/dl and mean C_{max} was 8545 mcg/dl, which were 1.67- and 1.42-fold higher than reported values in adults. The half-life of total serum iron was 8 hours[28].

Gender Differences

The effects of gender on the pharmacokinetics of iron sucrose have not been studied.

1.3 Clinical Data to Date

Several clinical studies were conducted by the manufacturer. One study was conducted in children. It was a randomized, open-label, dose-ranging study for iron maintenance treatment in pediatric patients with dialysis-dependent or non-dialysis-dependent CKD on stable erythropoietin therapy. The study randomized patients to one of three doses of Venofer (0.5 mg/kg, 1.0 mg/kg or 2.0 mg/kg). The mean age was 13 years (range 2 to 20 years). Over 70% of patients were 12 years or older in all three groups. There were 84 males and 61 females. About 60% of patients underwent hemodialysis and 25% underwent peritoneal dialysis in all three dose groups. At baseline, the mean hemoglobin was 12 g/dL, the mean TSAT was 33% and the mean ferritin was 300 ng/mL. Patients with HDD-CKD received Venofer once every other week for 6 doses. Patients with PDD-CKD or NDD-CKD received Venofer once every 4 weeks for 3 doses. Among 131 evaluable patients with stable erythropoietin dosing, the proportion of patients who maintained hemoglobin between 10.5 g/dL and 14.0 g/dL during the 12-week treatment period was 58.7%, 46.7%, and 45.0% in the Venofer 0.5 mg/kg, 1.0 mg/kg, and 2.0 mg/kg groups, respectively. A dose-response relationship was not demonstrated[28].

Since iron sucrose has been available for clinical use, it has been used in several research studies, two of these studies included children and adolescents with iron deficiency not related to underlying chronic renal failure [20, 21]. In one of these studies, 38 children were treated with parenteral iron sucrose for treatment of iron deficiency [20]. Five mild reactions were reported and included one patient with headache, two patients with abdominal pain, one patient with transient mild low blood pressure and one patient with fainting. In this study, one 15 year old

female had a serious allergic reaction that responded to treatment. This patient was treated with 500 mg of iron sucrose, which was above the recommended maximum dose of 300 mg. This study concluded that parenteral iron was a "safe and effective means to treat iron deficiency in children who cannot receive or do not respond to oral iron due to intolerance, poor adherence, or iron malabsorption" [20].

1.4 Dose Rationale and Risk/Benefits

Venofer®, an iron sucrose infusion preparation, has been approved by the U.S. Food and Drug Administration (FDA) for treatment of children and adolescents with iron-deficiency anemia and chronic kidney disease. The use of iron sucrose infusion is not FDA approved for the treatment of iron deficiency in adolescents with POTS.

In efficacy studies in non-dialysis dependent-chronic kidney disease patients (N=139), the most frequent adverse events (\geq 5%) whether or not related to Venofer® administration, were nausea (8.6%), taste disturbance (7.9%), peripheral edema (7.2%), diarrhea (7.2%), dizziness (6.5%), hypertension (6.5%), infusion site pain or burning (5.8%), dyspnea (5.8%), and vomiting (5.0%)[28]

In rare cases, serious hypersensitivity reactions, including anaphylactic-type reactions, some of which have been life-threatening and fatal, have been reported in patients receiving Venofer® (iron sucrose injection, USP). Patients may present with shock, clinically significant hypotension, loss of consciousness, and/or collapse[28].

Dexferrum®, an iron dextran infusion preparation, is FDA indicated for the treatment of children and adults with documented iron deficiency in whom oral administration is unsatisfactory or impossible. However, due to concerns for anaphylaxis reactions, iron dextran preparations have carried a FDA Black Box warning since 2009. Due to the improved safety profile of iron sucrose compared to iron dextran, iron sucrose has been selected as the iron infusion preparation for this study intervention. Iron sucrose does not carry a Black Box warning and does not require the pre-administration of medication test dose.

The dose selected for the study intervention is 5 mg/kg of Venofer® (iron sucrose) with a maximum dose of 200 mg. The dose will be diluted in normal saline 0.9% to a final concentration of 1 mg of elemental iron to 1 mL of normal saline 0.9%. In the study from Crary et al., doses up to 7 mg iron/kg up to a maximum dose of 300 mg were found to be safe and effective [20]. Five mild reactions were reported and included one patient with headache, two patients with abdominal pain, one patient with transient mild low blood pressure and one patient with fainting. One 15 year old female had a serious allergic reaction that responded to treatment. This patient was treated with 500 mg of iron sucrose, which was above the recommended maximum dose of 300 mg. In a similar study performed by Pinsk et al., doses of 5 mg iron/kg were used in pediatric patients and also found to be well tolerated with minimal adverse reactions [21].

In a single-dose pharmokinetics study of Venofer, patients with NDD-CDK ages 12 to 16 (N=11) received intravenous bolus doses of Venofer at 7 mg/kg (maximum 200 mg) administered over 5 minutes. Following single dose Venofer, the half-life of total serum iron was 8 hours[28].

•

In this pilot study, subjects will receive only one dose of iron sucrose.

Although adolescents are increasingly responsible for their health care decisions, there is an extensive literature highlighting poor prescription medication adherence in this population [18]. Oral iron supplements, in particular, are commonly discontinued due to patient complaints of gastric irritation and lack of palatability [19]. Nausea is also a common complaint of patients diagnosed with POTS, further complicating oral iron supplementation compliance. Given these limitations, intravenous iron supplementation has been used clinically for correction of iron deficiency in select adolescent patients.

2 Study Objectives

- 1. To assess whether a single infusion of iron sucrose will improve orthostatic symptoms as measured on a validated survey instrument in adolescent subjects with POTS and non-anemic iron deficiency
- 2. To assess whether a single infusion of iron sucrose will improve cardiovascular indices, specifically a reduction in heart rate change during a ten minute head up tilt, in adolescent subjects with POTS and non-anemic iron deficiency.
- 3. To determine if abnormalities in standing and supine catecholamine levels will improve following intravenous iron sucrose infusion in adolescent subjects with POTS and non-anemic iron deficiency

3 Study Design

3.1 General Design

This study is a randomized, double blind, placebo-controlled study to assess the efficacy of a single iron sucrose infusion in adolescents with non-anemic iron deficiency and POTS. Subjects will be screened at outpatient clinic visit appointments. Interested qualified subjects will be consented and offered participation in this trial. Once consent and assent (for patients less than 18 years of age) has been obtained, subjects will be randomized to either treatment or placebo group. Subjects will participate in two on site study visits. During the first visit subjects will complete baseline laboratory studies, tilt table test and study questionnaires. Subjects will then receive the intervention study drug or placebo. The second study visit will occur 7 days \pm 2 days from the first study visit. During the second study visit subjects will repeat laboratory studies, tilt table test and study questionnaires. Follow up questionnaires will be sent to all subjects six months following the initial study visit.

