4.2 Exclusion Criteria

- Orthostatic hypotension (decrease of systolic BP>30 mmHg and/or diastolic BP>15mmHg within 3 minutes of 70 degree head up tilt study)
- Pregnant or lactating females
- The presence of failure of other organ systems or systemic illness that can affect autonomic function
- Concomitant therapy with anticholinergic, alpha-adrenergic antagonists, betaadrenergic antagonists or other medications which could interfere with autonomic testing. Patients may participate if the potentially interfering medication is held for five half-lives prior to the study
- Laboratory evidence of anemia or iron overload
- Personal history of hematochromatosis or first degree relative with hematochromatosis
- Known sensitivity to Venofer® (iron sucrose injection, USP) or other intravenous iron preparation

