4.3 Subject Recruitment, Enrollment and Screening

Subjects will be recruited for this study from patients seen in the Department of Pediatric and Adolescent Medicine (DPAM) on the Mayo Clinic Rochester campus. The study will be advertised to medical providers within DPAM, particularly those practicing in the divisions of General Pediatrics and Adolescent Medicine (GPAM), Pediatric Neurology, Pediatric Cardiology, Pediatric Gastroenterology and Community Pediatrics and Adolescent Medicine (CPAM). Study information will be shared with these providers through verbal communication, printed materials and e-mail. The information will include inclusion and exclusion criteria, contact information for the Primary Investigator and study coordinator and brief study overview.

Patients will be screened by a study investigator or the study coordinator for review of study entry requirements.

Study enrollment and screening:

- 1. Will take place between 21 days and the day of first study visit
- 2. Will take place either at patient point of care or the Clinical Research Unit
- 3. Will review and document the following:
 - a. Consent and assent forms based on age of subject

- b. Subject demographics
- c. Physical exam by Mayo Clinic medical provider within 12 weeks of study enrollment
- d. Lab data (CBC, ferritin, total serum iron, percent iron saturation) within 12 weeks of study enrollment that meets inclusion and exclusion parameters
- e. Current medication review and compliance with exclusion parameters
- f. Randomization procedure to treatment or placebo group

Patients meeting the criteria will be offered participation in the study. A screening log will be kept to document reasons for ineligibility and for non-participation of eligible candidates. Those choosing to enroll will meet with a research study team member to complete the consent process. A research record will be generated for each study subjects. Documentation that the subject satisfied inclusion and exclusion criteria will be made.

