4.4 Early Withdrawal of Subjects

4.4.1 When and How to Withdraw Subjects

Subjects may stop their participation in the study at any time. Withdrawal of consent or assent will terminate the subject's participation in the study. The Principal Investigator will follow up with subjects to determine if ongoing medical management that may be indicated for patient safety as a result of study discontinuation. If the subject was in the treatment arm of the study, this may include follow up laboratory studies to assess laboratory response to therapy. Medical recommendations will be made by the Principal Investigator based on these results. The Principal Investigator will document reasons for subject dropout in the research record.

If a subject is withdrawn from the study, an additional subject may be enrolled to maintain the statistical power of the study.

In addition, the Principal Investigator or Mayo Clinic may stop the study at any time if there are severe adverse events or if adverse events are reported at a frequency higher than expected.

Subjects may be withdrawn from the study prior to completing all of the study if there is failure to adhere to the subject responsibility parameters.

Subject responsibility during study:

- 1. Subjects will be asked to stop taking medications that can potentially interact with tilt table test results at least 5 half-lives prior to study entry. This includes, but is not limited to anticholinergic, alpha-adrenergic antagonists and beta-adrenergic antagonists
- 2. Subjects will be asked to avoid caffeine and nicotine for at least 24 hours before each study site visit
- 3. Upon enrollment, subjects will be asked to discontinue iron supplements and/or vitamins containing iron until after the second study visit is complete
- 4. Subjects of child-bearing potential must have a negative urine beta-HCG (pregnancy test) prior to study entry
- 5. Subjects who are sexually active and able to become pregnant must agree to use one of the birth control methods listed below until after the last study site visit:
 - a. Hormonal methods, such as birth control pills, patches, injections, vaginal ring or implants
 - b. Barrier methods (such as a condom or diaphragm) used with a spermicide (a foam, cream, or gel that kills sperm)
 - c. Intrauterine device (IUD)
 - d. Abstinence (no sex)

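### Randomization may come up to 21 days before the Visit 1 eligibility checks and both primary baselines, so a subject lost in between is randomized with no dose and no change score

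*Combined protocol and SAP*

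**What the plan says.** **When allocation happens.** Three places agree.
- Section 3.1: after consent and assent, "subjects will be randomized to either treatment or placebo group". The on-site visits are described only after that.
- Section 4.3 lists "Randomization procedure to treatment or placebo group" as item f of enrollment and screening. On timing and place it says "Will take place between 21 days and the day of first study visit" and "Will take place either at patient point of care or the Clinical Research Unit".
- The schedule in Section 6 has one randomization mark, in the screening/enrollment column (day -21 to day 0).

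**What comes at Visit 1.** Section 3.1: "During the first visit subjects will complete baseline laboratory studies, tilt table test and study questionnaires". Section 6.1 orders the steps: eligibility review (a), vital signs (b), urine pregnancy test (c), COMPASS-31 and PedsQL (d), blood draw (e), tilt (f), symptom scale during the tilt (g), infusion (h). The schedule marks the pregnancy test at Visit 1 only.

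**Related rules.** Section 4.2 excludes "Pregnant or lactating females". Section 4.4.1 adds "Subjects of child-bearing potential must have a negative urine beta-HCG (pregnancy test) prior to study entry", without defining study entry. If a subject is withdrawn, 4.4.1 says "an additional subject may be enrolled to maintain the statistical power of the study". Sections 3.2 and 7.1 treat both the COMPASS-31 change and the tilt heart-rate change as primary, although 7.2 words the heart-rate hypothesis as secondary. Section 7.2 states that all analyses are by intention to treat.

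**The concern.** Under this order a subject can hold an allocation for up to three weeks before the protocol confirms eligibility, tests for a stated exclusion, or records either primary baseline. If the subject drops out or fails the Visit 1 review in that time, the trial has a randomized subject with no dose, no baseline and no change score. The missing-data paragraph in 7.2 describes data checking and gives no rule for a missing change score, and the only population that 7.3 defines requires study drug exposure. The analysis sections therefore have no place for such a subject.

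At stake is whether the analysed set equals the randomized set. In a trial of 15 per arm, each avoidable gap between the two is visible, and this kind of gap can largely be prevented by the order of steps within one visit.

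**Working it through.** **Inputs.** Enrollment window: 4.3 and the schedule. Step order and time estimates: 6.1. Replacement: 4.4.1. Target of 30 evaluable subjects: 7.1. The plan's 30 cannot be reproduced, because 7.1 gives no SD; it serves here only as the target number.

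**1. Length of the gap.** Day -21 to day 0 gives 0 to 21 days. Same-day enrollment is allowed but not required.

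**2. What is known at each possible allocation point.** Lead time is the sum of the 6.1 estimates for the steps left before infusion.

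| Allocation point | Already in hand | Still to come | Lead time |
|---|---|---|---|
| As planned | Enrollment labs, exam, medication review | Visit 1 review, pregnancy test, both primary baselines | 0 to 21 days before Visit 1 |
| After step d | Review, pregnancy test, COMPASS-31 | Visit 1 labs, baseline tilt | 20 (venipuncture) + 60 (tilt) = 80 min |
| After step g | All of these and both primary baselines | Infusion | 0 min |

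The difference between the last two rows matters. Section 4.1 requires a heart-rate rise of at least 40 bpm on tilt, and 4.2 excludes orthostatic hypotension on tilt. The screening list in 4.3 names no tilt, and the schedule first marks one at Visit 1. The documents do not say whether an earlier clinical tilt settles eligibility.

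**3. Completeness with full replacement.** If k subjects are lost in the gap and all are replaced to reach 30, the share of randomized subjects with primary baselines is 30/(30 + k). The k values are illustrations.
- k = 1: 30/31 = 96.8%
- k = 2: 30/32 = 93.8%
- k = 4: 30/34 = 88.2%

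If allocation follows the point of loss, the same departures leave 30/30.

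**4. Chance of at least one such subject.** For an assumed gap loss rate g among 30 randomized, this is 1 - (1 - g)^30: 45% at g = 2%, 79% at 5%, 96% at 10%, and 0 at g = 0. The documents support no particular g.

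**5. Pharmacy timing.** Tilts start between 12:00 and 16:00. Allocation after step d, 20 minutes earlier, falls at about 11:40 to 15:40. Allocation after step g, 60 minutes after tilt start, falls at about 13:00 to 17:00. Section 5.4 requires dilution and wrapping of bag and tubing but gives no preparation time. Early allocation is of limited use for preparation: 5.9.2 cites admixture stability of 7 days, so a bag could not be made up in the first 21 - 7 = 14 days of a full-length gap.

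**6. Reliability of the time estimates.** The Visit 1 items sum to 30 + 60 + 20 + 60 + (60 to 90) + 30 = 260 to 290 minutes, against a stated total of 4 to 4.5 hours (240 to 270 minutes). The 80 minutes is therefore approximate.

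**The case against.** **Eligibility is already screened at enrollment.** Section 4.3 requires labs that meet the criteria, a physical exam, a medication review and documentation that the criteria are met. The schedule also marks the criteria row at Visit 2, so the Visit 1 mark alone does not show an unscreened gap. This stands in part: most ineligibility should be caught before allocation. But 6.1 lists a fresh review as step a, no pregnancy test is scheduled at enrollment, and neither primary baseline exists yet.

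**The gap may be zero.** True, and then the effect may be nil. Even on day 0, though, randomization is listed under enrollment, ahead of the Visit 1 steps.

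**Replacement makes the number good.** This stands for the number analysed. It also answers a reader who infers a loss of precision. Using t(0.975, 2n - 2) × sqrt(2/n), going from 15 to 14 or 13 per arm widens a 95% interval by a factor of 1.039 or 1.082. That measures a failure to replace, not the timing: 30 can be analysed under either order. What replacement cannot supply is the lost subject's outcome, so the randomized set stays incomplete.

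**The pharmacy needs lead time.** This stands as a real constraint. The documents neither show that 80 minutes suffices nor that it does not.

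**Conclusion.** The sequencing point holds. As written, the plan can produce randomized subjects with no dose and no value for either primary outcome, and 4.4.1 repairs the count but not the completeness. The size is unknown, because no loss rate is given: nil if no one is lost in the gap, and 96.8% to 88.2% completeness for 1 to 4 replaced losses. This is an inexpensive improvement, not a defect that invalidates the trial.

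Three stronger readings are not supported:
- *Bias.* Sections 5.3, 5.4 and 5.8 plan for blinding, so losses in the gap should be unrelated to allocation.
- *Ineligible subjects being infused.* The review and pregnancy test both precede the infusion in 6.1.
- *Allocation after step d cures everything.* It secures the COMPASS-31 baseline but still precedes the baseline tilt. No choice of allocation point prevents losses between Visit 1 and Visit 2.

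**What to change.** Move the randomization mark in the schedule, and the matching wording in 3.1 and 4.3 item f, to Visit 1: before step h and as late as pharmacy preparation permits.
- Preferred: after the baseline tilt and symptom scale (steps f and g), so that both primary baselines and the tilt findings are in hand.
- At the earliest: after the eligibility review, negative pregnancy test and questionnaires (steps a to d).

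**Cost.** Wording in three places, with no change to assessments or sample size. The real cost is pharmacy lead time: about 80 minutes after step d, and little or none after step g unless the visit is lengthened. The research pharmacy should state its preparation time before the point is fixed, and the Visit 1 estimates should be reconciled with their stated total. An explicit analysis-set definition in 7.3 and a missing-data rule in 7.2 are worth having but are separate matters; this change does not depend on them.
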